The Efficacy and Safety of Silodosin Singly or Combined with Ningmitai Capsules in the Treatment of Benign Prostatic Hyperplasia (BPH) Complicated with Lower Urinary Tract Symptoms (LUTS) —A Multicenter, Prospective, Randomized, Doubleblind, Positive Controlled Study

Date: September 8, 2022

Research Proposal Summary

Scheme number	NM-22-A-001-YJ-001					
Scheme name	The Efficacy and Safety of Silodosin Capsules Singly or Combined with Ningmitai Capsules in the Treatment of Benign Prostatic Hyperplasia					
Version number/date	Version 1.0, December2, 2021					
sponsor	Shanghai Haitian Pharmaceutical Technology Development Co., Ltd.					
Clinical trial staging	Post-marketing clinical re-evaluation					
test drug	Ningmitai Capsules (Ningmitai [®] , Z20025442), each 0.38g, was produced by Guiyang Xintian Pharmaceutical Co., Ltd.					
	Silodosin Capsules (Qianweitai®, H20213612), each 4mg, was produced by Shanghai Huilun Pharmaceutical Co., Ltd.					
	Tamsulosin Hydrochloride Sustained Release Capsules(H20000681), each0.2mg, was produced by Astellas Pharma Inc.					
	Placebo, Ningmitai capsule simulator, each0.38g, was produced by Guiyang Xintian Pharmaceutical Co., Ltd.					
Indications	Benign Prostatic Hyperplasia with Lower Urinary Tract Symptom					
Test purposes	1.To evaluate the efficacy and safety of Silodosin Capsules alone versus Tamsulosin Hydrochloride Sustained Release Capsules in the treatment of BPH with lower urinary tract symptoms.					
	2.To evaluate the efficacy and safety of Ningmitai Capsules combination with Silodosin Capsules versus Silodosin Capsules alone in the treatment of BPH with lower urinary tract symptoms.					
Research design	A multicenter, prospective, randomized, controlled clinical trial design					
total number	It is planned to complete 312 cases (considering the 20% dropout rate)					
number of research	8					

centers					
Study period	6 months				
research	Diagnostic criteria:				
object	1. Male Subjects aged 60 ~ 80 years, clinically diagnosed as benign prostatic hyperplasia.				
	2. Has an IPSS score ≥ 8 points at Screening and Baseline.				
	3. Has a $4 \le Q_{max} \le 15$ ml/s when urination volume > 150 ml.				
	4. Has a prostate volume (PV) \geq 30 ml by ultrasound examination.				
	5. Subjects who can read, understand, and complete the research questionnaire.				
	6. Subjects willing to participate voluntarily in this clinical trial, give informed consent and sign				
	informed consent.				

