Group A: Tamsulosin combined with Ningmitai Capsules placebo. Oral Tamsulosin Hydrochloride Capsules (each 0.2mg), 1 capsule per time, 1 time a day. Oral Ningmitai Capsules placebo (each 0.38g), 4 capsules per time, 3 times a day. Continuous medication for 12 weeks.

Group B: Silodosin Capsules combined with Ningmitai Capsules placebo. Oral Silodosin Capsules (each 4mg), 1 capsule per time, 2 times a day. Oral Ningmitai Capsules placebo (each 0.38g), 4 capsules per time, 3 times a day. Continuous medication for 12 weeks.

Group C: Silodosin Capsules combined with Ningmitai Capsules. Oral Silodosin Capsules (each 4mg), 1 capsule per time, 2 times a day. Oral Ningmitai Capsules (each 0.38g), 4 capsules per time, 3 times a day. Continuous medication for 12 weeks.

Combined medication

Combination drugs banned during the study:

- (1) CYP3A4 inhibitors (eg. Ketoconazole, Clarithromycin, Itraconazole, Ritobuvir)
- (2) Other α-receptor blockers besides this study and other drugs with therapeutic effects on BPH include 5-α reductase inhibitors, phosphodiesterase type 5 (PDE-5) inhibitors, M receptor blockers, β3 receptor agonists, botanical drugs or traditional Chinese medicines, etc.

Combination drugs used with caution during the study:

- (1) Strong inhibitors of CYP2D6 (such as Paroxetine) may lead to a significant increase in exposure to Tamsulosin.
- (2) Potential P-glycoprotein (P-gp) inhibitors (such as Cyclosporin), in vitro studies have shown that Silodosin is a P-gp substrate, and the inhibition of P-gp may lead to an increase in the blood concentration of Silodosin.
- (3) Antihypertensive drugs, there is a decline in blood pressure regulation ability when standing up and pay close attention to blood pressure changes when combined with α -receptor blockers.
- (4) Drugs that may induce or aggravate urinary retention, such as Anticholinergic Atropine, Antiallergic Chlorpheniramine, Antidepressant Imipramine, and ready-for-use traditional Chinese

medicine or decoction containing ephedra.

Concomitant drugs allowed during the study period:

If the subjects have basic diseases and need to take drugs for a long time, and they are not prohibited drugs in this study, they can continue to use them during the study period.

If the subject has adverse reactions, it is up to the researcher to decide whether to use symptomatic treatment drugs.

All drugs used at the same time should be recorded and explained in detail on CRF table.

Treatment and

follow-up

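### The double-blind label is not supported, as the arms are written, for the primary silodosin versus tamsulosin non-inferiority comparison

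*Protocol*

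**What the plan says.** The protocol title describes the study as "A Multicenter, Prospective, Randomized, Doubleblind, Positive Controlled Study", and the SAP title makes the same claim. The Research design row of the protocol lists other design features but is silent on blinding.

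The Trial grouping and medication row, repeated in the SAP, defines the arms:

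- Group A, alpha-blocker: "Oral Tamsulosin Hydrochloride Capsules (each 0.2mg), 1 capsule per time, 1 time a day".
- Groups B and C, alpha-blocker: "Oral Silodosin Capsules (each 4mg), 1 capsule per time, 2 times a day".
- Groups A and B, placebo: "Oral Ningmitai Capsules placebo (each 0.38g), 4 capsules per time, 3 times a day".
- Group C, active Ningmitai: "Oral Ningmitai Capsules (each 0.38g), 4 capsules per time, 3 times a day".

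The test drug row lists the two alpha-blockers as separate products from separate manufacturers: "Silodosin Capsules (Qianweitai®, H20213612), each 4mg, was produced by Shanghai Huilun Pharmaceutical Co., Ltd" and "Tamsulosin Hydrochloride Sustained Release Capsules(H20000681), each0.2mg, was produced by Astellas Pharma Inc". It lists one placebo, the Ningmitai simulator. The Research steps row likewise gives Groups A and B one placebo each.

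SAP section 2(1) makes silodosin versus tamsulosin (B versus A) a non-inferiority test on the change in IPSS at 12 weeks, at one-sided 0.025. Section 2(3) sets the margin at 1 point.

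**The concern.** A placebo masks a comparison only if it stands in for something that differs between the two arms. Groups A and B take the same simulator at the same count and frequency, so it hides nothing between them. What differs is the alpha-blocker, taken once a day in A and twice a day in B, and nothing listed covers that difference. Anyone who knows the regimens and sees a patient's intake or supply can tell A from B.

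Silodosin versus tamsulosin is the first stated purpose of the trial and one of its two primary comparisons. The outcome is a symptom score. The Research steps row says that scales are scored at visits, but not by whom or under what masking. Inclusion criterion 5 requires patients to be able to fill in the study questionnaire; this fits patient-reported scoring, although it does not name IPSS. If the plan is followed as written, the result would be published under a title that claims a protection the described arms do not provide. That affects how the result may be described and how far a reader can rely on it.

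**Working it through.** The plan gives no calculated figure on this point, so the check is a capsule count by arm followed by a comparison of pairs. Inputs are the capsules per intake and intakes per day from the Trial grouping and medication row, and the placebos in the test drug row.

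Capsules per day = capsules per intake × intakes per day.

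| | Group A | Group B | Group C |
|---|---|---|---|
| Alpha-blocker | 1 × 1 = 1 (tamsulosin) | 1 × 2 = 2 (silodosin) | 1 × 2 = 2 (silodosin) |
| Ningmitai simulator | 4 × 3 = 12 | 4 × 3 = 12 | 0 |
| Active Ningmitai | 0 | 0 | 4 × 3 = 12 |
| Dummy alpha-blocker | 0 | 0 | 0 |
| Total | 1 + 12 = 13 | 2 + 12 = 14 | 2 + 12 = 14 |

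**A versus B.** Simulator: 12 − 12 = 0, so it contributes nothing to masking this pair. Alpha-blocker: 1 − 2 = −1 capsule a day, one intake against two, with a different product. None of this is covered.

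**B versus C.** Alpha-blocker: 2 − 2 = 0, with the same product and schedule. The only difference is 12 simulator capsules against 12 Ningmitai capsules, which is what a matching simulator is meant to hide. This pair can be masked as written, provided the simulator does match.

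**Other masking devices.** Apart from the two titles, the documents supplied do not mention blinding. They describe no double-dummy, common outer capsule, blinded packaging, separate dispenser or blinded assessor. A dummy alpha-blocker would be expected in the test drug row, the arm descriptions and the Research steps row, and it is in none of them.

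Capsule appearance is not described and need not be assumed. Dosing frequency alone separates A from B for someone who knows both regimens.

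**The case against.** The strongest reply is that this argues from silence in a condensed document. The protocol is headed "Research Proposal Summary", and the SAP repeats the same table. Neither has a section on blinding, packaging or dispensing, so a dummy or over-encapsulation could exist without appearing here. Even the B versus C masking is described only through the simulator entry. This stands as a limit: the documents do not show that A versus B was run unmasked. It does not remove the mismatch. The summary is specific about placebo, giving its strength, manufacturer, count and frequency, and names only one.

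Second, each patient sees only his own regimen, so one or two intakes a day reveals nothing to a patient who does not know the alternative. That is fair, because what patients are told is not visible. However, site staff working from this protocol would know the regimens, and anyone instructing a patient on frequency would learn whether he is in A or in B/C. A double-blind label has to cover staff as well.

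Third, no bias is quantified and no test, margin or sample size changes, so this might be only a request for clarification. It is true that no bias is quantified. But if no masking device exists, the permissible description of a primary result changes, and that goes beyond missing detail.

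**Conclusion.** The concern holds. The listed placebo covers the whole of the B versus C difference and none of the A versus B difference (simulator 12 against 12; alpha-blocker intake once against twice a day; dummy alpha-blocker capsules 0 in every arm). As written, the double-blind label is unsupported for one of the two primary comparisons; the other is unaffected, assuming the simulator matches Ningmitai.

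The conclusion rests on the arm rows and drug list being complete as to what patients take. Confidence is medium because masking recorded in a fuller document cannot be ruled out. The size and direction of any bias cannot be estimated from the documents, and none is claimed. The silence of the Research design row is an omission, not a contradiction. The mismatch should be corrected before the A versus B result is reported.

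**What to change.** Reconcile both titles and the Research design row with the arms and the drug list, and state who is blinded and how.

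1. **If a masking device for A versus B exists:** add it to the test drug row and to the arm descriptions in both documents, and name the blinded roles.
2. **If the sponsor confirms that none exists:** limit the double-blind claim to B versus C, and state that the simulator matches Ningmitai. State that A versus B is not masked to the alpha-blocker regimen, and which roles, if any (for example outcome assessors or analysts), remain blinded. Then add to SAP section 2(3):

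> The Silodosin + placebo versus Tamsulosin + placebo comparison was not masked to the alpha-blocker regimen; [roles] remained blinded. The non-inferiority result is reported with this limitation and not as double-blind evidence.

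That sentence applies only under option 2. Neither option changes an active dose or schedule, the margin, the alpha level or the sample size. The cost is wording in the titles, the Research design row, and the drug list or arm rows, plus one addition to the SAP under option 2. Option 2 leaves the trial with a less favourable design label; it corrects the description but does not remove any bias.

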The Efficacy and Safety of Silodosin Singly or Combined with Ningmitai Capsules in the Treatment of Benign Prostatic Hyperplasia (BPH) Complicated with Lower Urinary Tract Symptoms (LUTS) —A Multicenter, Prospective, Randomized, Double-blind, Positive Controlled Study

Date: September 8, 2022

Statistical analysis Plan

1.Statistical analysis of population:

- (1) **FAS:** According to the basic principle of intentionality analysis (ITT), all the randomized subjects with more than one medication record and effectiveness evaluation were included in the full analysis set. The total analysis set is the main validity evaluation population of this study.
- (2) **PPS:** Include all subjects who have completed the treatment stipulated in the scheme or have not seriously violated the trial scheme. The exact definition of the serious violation scheme will be finalized during the data review. PPS is the secondary analysis population of validity, but if its results are inconsistent with the full analysis set, it is necessary to analyze the inconsistent results in detail.
- (3) **SS:** Defined as all subjects who were randomized and received at least one trial drug treatment. The safety analysis set is the safety evaluation population of this study.

2.Statistical analysis method:

- (1) **General principle:** All statistical analysis shall be processed by SPSS 23.0 and above statistical software, and shall be carried out according to the pre-established statistical analysis plan. Measurement data are described by mean, standard deviation, median, quartile, maximum and minimum. The counting data are described by frequency and percentage. After 12 weeks of treatment, the changes of IPSS scores between Tamsulosin + placebo group and Silodosin + placebo group were compared by non-inferior test, while the changes of IPSS scores between Ningmitai + Silodosin group and Silodosin + placebo group were compared by superior test, and the test levels were $\alpha = 0.025$ (unilateral). Other hypotheses were tested by two-side test with a test level of $\alpha=0.05$, and the secondary index was adjusted by Bonferroni method with a test level of $\alpha=0.0167$.
- (2) **Balance analysis of baseline value:** Comparability analysis of demographic characteristics, general situation and baseline situation (before treatment) of the two groups of data. Among them, t test or Wilcoxon rank sum test was used for measurement data and grade data, and χ^2 test or Fisher exact probability method was used for classification data.
- (3) **Effectiveness analysis:** Conducted in FAS and PPS at the same time.

① **Main endpoint indicators:** After 12 weeks of treatment, the difference of IPSS score decline and 97.5% CI of the three groups were calculated. If the lower limit of unilateral 97.5% confidence interval of the difference of IPSS score decline between Silodosin + placebo group and Tamsulosin + placebo group is greater than the non-inferiority threshold of 1 (-1 point), then "Silodosin + placebo" is not inferior to "Tamsulosin + placebo" group. If the lower limit of unilateral 97.5% confidence interval of the difference between the IPSS scores of Silodosin + Ningmitai group and Silodosin + placebo group is greater than the superior effect threshold of 2 (0 points), then "Silodosin + Ningmitai" is superior to "Silodosin +

placebo". Subgroup analysis was considered according to whether the NIH-CPSI pain score was ≥ 4 before treatment and the severity of IPSS total score.

②Secondary endpoint index: The changes of IPSS scores, IPSS sub-scores and QoL scores were compared between groups at 1, 2, 4, 8 and 12 weeks after treatment. The changes of Q_{max} , PVR, serum PSA and prostate volume were compared between groups by single factor analysis of variance or Wilcoxon rank sum test. Bonferroni method was used to adjust the test $\alpha = 0.0167$. The clinical progression curve of BPH was drawn by Kaplan-Meier; COX regression model was used to compare the factors affecting the clinical progression of BPH. The proportion of patients with IPSS total score decreased in severity was compared between groups by χ^2 test or Fisher exact probability method.

(4) Security analysis: To evaluate the safety of SS population. The data of safety evaluation include the adverse events observed during the trial and the changes of laboratory examination data before and after treatment. Descriptive statistics were used for adverse events, and the total incidence of adverse events and the incidence of various adverse events were compared among each group. In addition to comparing the average data before and after treatment, the laboratory examination data mainly analyzed and listed the specific situation of normal cases before treatment and abnormal cases after treatment or abnormal cases before treatment and abnormal cases after treatment.

centers	
Study period	6 months
research	Diagnostic criteria:
object	
 1. Male Subjects aged 60 ~ 80 years, clinically diagnosed as benign prostatic hyperplasia. 2. Has an IPSS score ≥ 8 points at Screening and Baseline. 3. Has a $4 \leq Q_{\max} \leq 15$ ml/s when urination volume > 150 ml. 4. Has a prostate volume (PV) ≥ 30 ml by ultrasound examination. 5. Subjects who can read, understand, and complete the research questionnaire. 6. Subjects willing to participate voluntarily in this clinical trial, give informed consent and sign informed consent.
	Exclusion criteria:
	
 1. Subjects with prostate cancer or other malignant tumors. 2. Subjects have serum tPSA > 10 ng/ml, or $4 \leq tPSA \leq 10$ ng/ml while fPSA/tPSA < 0.16 times. 3. Subjects suffered from other diseases causing dysuria, such as bladder neck spasm, urethral stricture, neurogenic bladder dysfunction, etc. 4. Subjects have suffered from acute urinary retention, or complicated with gross hematuria, urinary tract infection, bladder stones, secondary upper urinary tract hydronephrosis, urinary incontinence, renal insufficiency and other subjects that researchers believe meet the surgical indications. 5. Subjects have undergone prostate surgery, microwave therapy, urethral dilatation or acute urinary retention catheterization or other invasive procedures. 6. Subjects have residual urine volume (PVR) > 100 ml, or those who may have urinary retention and need catheterization. 7. Subjects who took α receptor blockers, traditional Chinese Medicine or botanical drugs for treating BPH within two weeks before participating this clinical trial. 8. Subjects who take 5α reductase inhibitor or other antiandrogen therapy drugs within half a year before participating this clinical trial. 9. Subjects who need to take drugs prohibited in this study or adopt prohibited treatment methods during treatment. 10. Subjects who Complicated with severe cardiovascular and cerebrovascular diseases, respiratory diseases, blood diseases, liver, and kidney diseases. 11. There are significant abnormalities in clinical or laboratory examination indexes of patients,

	
such as ALT and AST \geq 2.5 times of the upper limit of reference value, creatinine (Scr) $>$ 1.5 times of the upper limit of reference value, or poor blood glucose control (fasting blood glucose FPG \geq 10 mmol/L).
 
12. Subjects who are allergic to the drugs or ingredients used in the test definitely.
 
13. Any other Subjects in the opinion of researchers is not suitable for inclusion.

Trial grouping and medication	
According to the random sequence generated by computer, eligible patients were randomly assigned to three groups according to 1: 1: 1.
 
Group A: Tamsulosin combined with Ningmitai Capsules placebo. Oral Tamsulosin Hydrochloride Capsules (each 0.2mg), 1 capsule per time, 1 time a day. Oral Ningmitai Capsules placebo (each 0.38g), 4 capsules per time, 3 times a day. Continuous medication for 12 weeks.
 
Group B: Silodosin Capsules combined with Ningmitai Capsules placebo. Oral Silodosin Capsules (each 4mg), 1 capsule per time, 2 times a day. Oral Ningmitai Capsules placebo (each 0.38g), 4 capsules per time, 3 times a day. Continuous medication for 12 weeks.
 
Group C: Silodosin Capsules combined with Ningmitai Capsules. Oral Silodosin Capsules (each 4mg), 1 capsule per time, 2 times a day. Oral Ningmitai Capsules (each 0.38g), 4 capsules per time, 3 times a day. Continuous medication for 12 weeks.

Combined medication	
Combination drugs banned during the study:
 
 (1) CYP3A4 inhibitors (eg. Ketoconazole, Clarithromycin, Itraconazole, Ritobuvir) (2) Other α-receptor blockers besides this study and other drugs with therapeutic effects on BPH include 5-α reductase inhibitors, phosphodiesterase type 5 (PDE-5) inhibitors, M receptor blockers, β3 receptor agonists, botanical drugs or traditional Chinese medicines, etc. 
Combination drugs used with caution during the study:
 
 (1) Strong inhibitors of CYP2D6 (such as Paroxetine) may lead to a significant increase in exposure to Tamsulosin. (2) Potential P-glycoprotein (P-gp) inhibitors (such as Cyclosporin), in vitro studies have shown that Silodosin is a P-gp substrate, and the inhibition of P-gp may lead to an increase in the blood concentration of Silodosin. (3) Antihypertensive drugs, there is a decline in blood pressure regulation ability when standing up and pay close attention to blood pressure changes when combined with α-receptor blockers. (4) Drugs that may induce or aggravate urinary retention, such as Anticholinergic Atropine, Antiallergic Chlorpheniramine, Antidepressant Imipramine, and ready-for-use traditional Chinese

	
medicine or decoction containing ephedra.
 
Concomitant drugs allowed during the study period:
 
If the subjects have basic diseases and need to take drugs for a long time, and they are not prohibited drugs in this study, they can continue to use them during the study period.
 
If the subject has adverse reactions, it is up to the researcher to decide whether to use symptomatic treatment drugs.
 
All drugs used at the same time should be recorded and explained in detail on CRF table.

Treatment and follow-up	
Course of treatment: 12 weeks
 
Visit points: screening period, days -28 to 0), after 1 week of treatment (day 7±2), after 2 weeks of treatment (day 14±3), after 4 weeks of treatment (day 28±5), after 8 weeks of treatment (day 56±7), after 12 weeks of treatment (day 84±10).

Research steps	
This trial is divided into two stages: screening period, treatment period and follow-up period.
 
Screening period (days -28 to 0): After signing the informed consent form, the subjects entered the screening period, and made a 24-hour urination diary and screening examination.
 
Treatment and Follow-up period: eligible patients were randomly assigned to three groups according to 1: 1: 1 and received Tamsulosin + placebo, Silodosin + placebo or Silodosin + Ningmitai for 12 weeks. During the treatment period, the subjects' diaries were recorded according to the requirements of the scheme, and they were followed up at 1 week (7±2 days), 2 weeks (14±3), 4 weeks (28±5 days), 8 weeks (56±7 days) and 12 weeks (84±10 days). During the visit, relevant scale scores and laboratory examinations were performed, and the occurrence of adverse events during the follow-up was recorded to evaluate the safety.

study endpoint	
Primary endpoint:
 
International Prostate Symptom Score (IPSS), Changes of scores at the 12th week of treatment compared to the baseline scores.
 
Secondary endpoints:
 
1. IPSS Score
 
① changes of IPSS total score: Changes of IPSS scores at 1, 2, 4 and 8 weeks after treatment compared with baseline scores
 
② Proportion of patients with IPSS total score severity decreased by at least one grade at 12 weeks
 
③ IPSS sub-score: IPSS Stimulation Score at 1, 2, 4, 8, 12 weeks (Sum of Question 2, 4, 7) and


Changes of IPSS obstruction score (sum of question 1, 3, 5, 6) compared with baseline.
 
2. Quality of life (QoL) score: Changes in scores at 4, 8 and 12 weeks of treatment compared with baseline
 
3. Maximum urinary flow rate (Q_{max})
 
The change of Q_{max} at 12 weeks of treatment compared with baseline.
 
4. Patient response rate
 
Patient response rate is defined as the proportion of patients whose IPSS total score decreased by $\geq 25\%$ and Q_{max} increased by $\geq 30\%$ compared with baseline value after treatment.
 
5. Residual urine volume (PVR)
 
Changes of PVR at 12 weeks of treatment compared with baseline.
 
6. Prostate specific antigen (PSA)
 
Changes of PSA at 12 weeks of treatment compared with baseline.
 
7. Prostate volume (PV)
 
Changes of PV at 12 weeks of treatment compared with baseline.
 
8. Proportion of patients with BPH clinical progression
 
Clinical progress is defined as the first occurrence of one of the following two conditions during the trial:
 
 ① Acute urinary retention (AUR). ② Clinical diagnosis requires surgical treatment of BPH. 
Subgroup analysis:
 
Patients were grouped according to the following conditions of subjects at baseline, and the therapeutic effect of curative effect indicators was evaluated among different subgroups to determine whether the therapeutic effect was consistent among subgroups:
 
 ① The scores of IPSS were moderate (8-19) and severe (20-35); ② Routine examination of EPS (EPS leukocytes > 4HP or < 4HP. If EPS is not collected after prostate massage, it is not advisable to repeat massage for many times, and it is recommended to take urine after prostate massage for analysis.). ③ Symptoms of chronic prostatitis (NIH-CPSI pain score ≥ 4 and < 4)

security indicators	
The incidence of adverse drug events/reactions was calculated according to the following indicators:
 
1.Vital signs: Blood pressure, heart rate2.Laboratory examination index: Blood routine, Urine routine, liver function (ALT, AST, ALP) and renal function (BUN, Scr).3.Possible adverse drug events/reactions.
--------------------------------	--

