Course of treatment: 12 weeks

Visit points: screening period, days -28 to 0), after 1 week of treatment (day 7 ± 2), after 2 weeks of treatment (day 14 ± 3), after 4 weeks of treatment (day 28 ± 5), after 8 weeks of treatment (day 56 ± 7), after 12 weeks of treatment (day 84 ± 10).

Research steps

This trial is divided into two stages: screening period, treatment period and follow-up period.

Screening period (days -28 to 0): After signing the informed consent form, the subjects entered the screening period, and made a 24-hour urination diary and screening examination.

Treatment and Follow-up period: eligible patients were randomly assigned to three groups according to 1: 1: 1 and received Tamsulosin + placebo, Silodosin + placebo or Silodosin + Ningmitai for 12 weeks. During the treatment period, the subjects' diaries were recorded according to the requirements of the scheme, and they were followed up at 1 week (7 ± 2 days), 2 weeks (14 ± 3), 4 weeks (28 ± 5 days), 8 weeks (56 ± 7 days) and 12 weeks (84 ± 10 days). During the visit, relevant scale scores and laboratory examinations were performed, and the occurrence of adverse events during the follow-up was recorded to evaluate the safety.

study endpoint

Primary endpoint:

International Prostate Symptom Score (IPSS), Changes of scores at the 12th week of treatment compared to the baseline scores.

Secondary endpoints:

1.IPSS Score

- ①changes of IPSS total score: Changes of IPSS scores at 1, 2, 4 and 8 weeks after treatment compared with baseline scores
- ②Proportion of patients with IPSS total score severity decreased by at least one grade at 12 weeks
- ③IPSS sub-score: IPSS Stimulation Score at 1, 2, 4, 8, 12 weeks (Sum of Question 2, 4, 7) and

Changes of IPSS obstruction score (sum of question 1, 3, 5, 6) compared with baseline.

- 2.Quality of life (QoL) score: Changes in scores at 4, 8 and 12 weeks of treatment compared with baseline
- 3. Maximum urinary flow rate (Q_{max})

The change of Q_{max} at 12 weeks of treatment compared with baseline.

4. Patient response rate

Patient response rate is defined as the proportion of patients whose IPSS total score decreased by \geq 25% and Q_{max} .

increased by $\geq 30\%$ compared with baseline value after treatment.

5. Residual urine volume (PVR)

Changes of PVR at 12 weeks of treatment compared with baseline.

6. Prostate specific antigen (PSA)

Changes of PSA at 12 weeks of treatment compared with baseline.

7. Prostate volume (PV)

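### The primary week-12 IPSS analysis is a bare difference with no model, no baseline covariate and no rule for subjects without a week-12 value, although IPSS is scheduled at four earlier visits

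*SAP*

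**What the plan says.** - **Endpoint.** The Protocol's primary endpoint is the IPSS total: "Changes of scores at the 12th week of treatment compared to the baseline scores". The first secondary endpoint uses the IPSS total at weeks 1, 2, 4 and 8, so these values are already to be collected.
- **Population.** SAP 1(1) invokes the ITT principle and states that "all the randomized subjects with more than one medication record and effectiveness evaluation were included in the full analysis set". The FAS is the main efficacy population. No visit is attached to the effectiveness evaluation.
- **Primary analysis.** SAP 2(3) ① begins "After 12 weeks of treatment, the difference of IPSS score decline" and adds a 97.5% CI. The lower limit is compared with -1 for silodosin (B) against tamsulosin (A), and with 0 for the combination (C) against silodosin (B). No test, model, covariate or handling of missing values is named.
- **Earlier visits.** They appear only in the secondary analysis, SAP 2(3) ②: "The changes of IPSS scores, IPSS sub-scores and QoL scores were compared between groups at 1, 2, 4, 8 and 12 weeks after treatment".
- **Robustness.** Efficacy analysis is "Conducted in FAS and PPS at the same time". SAP 1(2) adds: "PPS is the secondary analysis population of validity, but if its results are inconsistent with the full analysis set", the differences must be examined in detail. No missing-data sensitivity analysis is given.
- **Dropout.** The Protocol plans 312 cases, "considering the 20% dropout rate".

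**The concern.** Two things are left open in the same sentence of the SAP.

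The first is precision. A plain difference in change scores ignores baseline IPSS and the four intermediate visits. The non-inferiority margin is only 1 point, so the width of the interval matters.

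The second is missing week-12 values. Analysing observed values only, carrying the last value forward, and fitting a likelihood model all comply with the text. If dropout is related to response in one arm only, these choices are biased differently. The FAS-PPS comparison would not reveal this under an observed-value analysis, because a subject without a week-12 score contributes to neither estimate. The same applies to C against B.

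**Working it through.** **Inputs from the documents:** 312 subjects, 1:1:1, so 104 per arm; 20% dropout; margin -1 for B-A and threshold 0 for C-B; one-sided alpha 0.025; IPSS at baseline and weeks 1, 2, 4, 8 and 12.

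**Assumed, because the documents give none:** SD of change 2.5, 3 or 5; true B-A of 0 for power; correlation between visits; dropout after week 4.

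**1. The plan's own figure.** The 312 cannot be reproduced, since no SD, expected difference or power is stated. Only the dropout step can be checked: 83 / 0.80 = 103.75, rounded up to 104 per arm, and 3 x 104 = 312. But 86 x 1.20 = 103.2 also rounds up to 104, so neither derivation is established.

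**2. Subjects affected.** 312 x 0.20 = 62.4 in total, leaving 104 x 0.80 = 83.2 per arm. If 312 means completers, 312 / 0.80 = 390 are randomized and 390 - 312 = 78 may drop out.

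**3. Choice of SDs.** For 80% power at a true difference of 0, SD = sqrt(n/2) / (1.960 + 0.842). This is 2.30 with 83 per arm and 2.57 with 104. SD 2.5 is therefore near what a trial of this size would need; 3 and 5 show less favourable cases.

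**4. Precision, same dropout pattern in both arms.** With 83 observed per arm, SE = SD x sqrt(2/83) and power = Phi(1/SE - 1.96). With equal variances and baseline-to-week-12 correlation r, adjusting for baseline multiplies the SE by sqrt((1 + r)/2), which is 0.866 at r = 0.5.

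| SD | SE, plain | Power, plain | SE, adjusted | Power, adjusted |
|---|---|---|---|---|
| 2.5 | 0.388 | 73% | 0.336 | 85% |
| 3 | 0.466 | 57% | 0.403 | 70% |
| 5 | 0.776 | 25% | 0.672 | 32% |

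Simulated trials (104 per arm, 20% dropout after week 4) agree:

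| SD | Plain observed values | Baseline-adjusted observed values | Repeated-measures model |
|---|---|---|---|
| 2.5 | 74% | 84% | 86% |
| 3 | 57% | 69% | 69% |
| 5 | 27% | 32% | 31% |

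Differences of a point or two between columns are within simulation error. Nearly all the gain is baseline adjustment; the intermediate visits add little here. Observed-value bias stays within 0.04.

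**5. Bias if dropout differs between arms.** With 20% missing in each arm, the observed-value estimate is off by 0.2 x (between-arm difference in the missing minus that in the observed). Assumed gaps of 1 to 5 points give 0.2 to 1.0 points. In simulation, B loses poor early responders and A loses subjects at random:

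| SD | Observed-value bias towards silodosin | Carry-forward bias |
|---|---|---|
| 2.5 | 0.09 to 0.25 | not tabulated |
| 3 | 0.12 to 0.36 | -0.23 to +0.05 |
| 5 | 0.33 to 0.82 | -0.50 to +0.02 |

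At a true B-A of -1, observed values then give false non-inferiority in 4-11% of trials at SD 3 and 6-19% at SD 5, against a nominal 2.5%. If tamsulosin loses the poor responders instead, the observed-value bias reverses. The model's bias is within 0.04, as expected where dropout depends only on observed scores.

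**6. Where the model is not protected.** If dropout in B depends on the unseen week-12 score, the bias is 0.12-0.34 for the model against 0.26-0.55 for observed values at SD 3, and 0.30-0.78 against 0.67-1.24 at SD 5.

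**The case against.** Several objections have force.

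- **The power gain is not a missing-data effect.** Baseline-adjusted observed values alone recover nearly all of it. A reader might infer that the absent missing-data rule costs the power; it does not. The loss comes from the unadjusted difference. Nor does using observed values only rule out baseline adjustment: these are separate choices, and the SAP states neither.
- **Changing verdicts are not specific to dropout.** Observed-value and carry-forward analyses of the same simulated data reach different non-inferiority verdicts in 9-23% of trials, which might suggest that dropout handling decides the result. But adjusted and unadjusted analyses of the same observed values differ about as often, roughly 15-18%. This supports naming one analysis in advance and says nothing particular about missing data.
- **The larger biases need informative dropout in one arm only.** Nothing in the documents predicts that.
- **The 20% is a planning allowance.** Subjects who leave before any effectiveness evaluation fall outside the FAS, so 62 is an upper figure at that rate.
- **A fuller plan may exist.** The Protocol is a proposal summary, and SAP 2(1) says that analysis "shall be carried out according to the pre-established statistical analysis plan". If the rule is held elsewhere, it only needs to be copied in.

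What stands: neither document names the model, the covariate or the rule.

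**Conclusion.** The point holds as a weakness in the stated primary method. Taken as written, with a plain difference of observed values, the analysis gives up about 12 percentage points of non-inferiority power at SD 2.5 (86 - 74) and at SD 3 (69 - 57), and about 4 at SD 5 (31 - 27). The cause is mainly the missing baseline adjustment.

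The lack of a rule for week-12 values is a separate and conditional risk: negligible if the arms drop out alike, and a sizeable part of the 1-point margin if they do not. A reader might conclude that the planned analysis is biased or that non-inferiority would be falsely declared. The documents do not support that, since they give no reason to expect differential dropout. They simply contain no protection against it.

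The direction of these results is firm. The sizes rest on assumed SDs, correlations and dropout timing.

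**What to change.** In SAP 2(3) ①, make the FAS primary analysis a mixed model for repeated measures on IPSS change at weeks 1, 2, 4, 8 and 12. Terms: treatment, visit, treatment-by-visit, baseline IPSS and baseline-by-visit, with unstructured covariance. SPSS MIXED, within the software already named, can fit it. Compare the lower limits of the week-12 contrasts B-A and C-B with -1 and 0. State whether IPSS recorded after a subject stops study drug is included.

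Add one sensitivity analysis per contrast, by multiple imputation of missing week-12 values under its null: B 1 point worse than A; C equal to B.

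**Cost.** SAP text and slightly more analysis work; no new visits, data or subjects.

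**Limits.** The model assumes missing at random and does not recover subjects with no post-baseline IPSS. If dropout depends on the unseen score, it only reduces the bias. The sensitivity analyses offset only part of the remainder. With 20% missing, B-A becomes 0.8 x estimate + 0.2 x (-1), a shift of 0.2 x (estimate + 1), or 0.2 points at an estimate of 0. C-B shrinks by about 20%.
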